#### **5.4.5. Apremilast Subjects as Treated Population**

The safety analysis for an apremilast-exposure period will be based on the apremilast subjects as treated population, which will include all subjects who are randomized (at Week 0) or assigned (at Week 12) to an apremilast dose group, and receive at least 1 dose of apremilast. At least 1 post-baseline assessment is required for inclusion in the analysis of each specific laboratory, vital sign, weight, or ECG parameter. To assess change from baseline, a baseline measurement is also required. Subjects will be included in the apremilast dose group corresponding to the apremilast dose they actually received.

## 6. SUBJECT DISPOSITION

The number of subjects screened, the numbers and percentages of subjects randomized and not randomized, and of the eligibility criteria failed will be summarized based on all subjects screened.

The number and percentage of subjects included in the analysis populations will be summarized based on all subjects randomized.

Subject disposition (entered, completed, discontinued, along with primary reason for discontinuation) will be summarized based on all subjects randomized, unless otherwise specified below, for

- Weeks 0-12
- Weeks 0-52
- Weeks 12-52 (based on subjects who complete Week 12)
- Weeks 52-104 (based on subjects who enter the Extension Phase)
- Post-treatment observational follow-up phase (entered and completed only) within each of the above periods (based on subjects who enter the respective period)

The definitions of entry and completion in the above disposition summaries are given in [Table 2](#).

**Table 2: Definitions of Entry and Completion in Disposition Summaries**

Disposition Category	Weeks 0-12	Weeks 0-52	Weeks 12-52	Weeks 52-104	Follow-up Phase
Entered	Randomized	Randomized	Completed Week 12/Visit 6	Completed Week 52/Visit 11 and indicated continuation into Extension Phase in eCRF	Indicated continuation into Follow-up Phase in eCRF and had data after the last non-follow-up visit (Week 104/Visit 14 or ET visit, excluding any unscheduled visits associated with Week 104/Visit 14 and ET visit)
Completed	Completed Week 12/Visit 6	Completed Week 52/Visit 11	Completed Week 52/Visit 11	Completed Week 104/Visit 14	Completed the follow-up visit

A listing of discontinued subjects with reason for discontinuation will be provided.

The number and percentage of subjects by region, country, and site will be provided based on all subjects randomized.

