| SF-12v2 (Short Form 12-item Health Survey, version 2) | - | X | - | - | - | X | - | - | - | - | X | - | - | X | - | - |
| CCI | | | | | | | | | | | | | | | | |
| Dispense IP | - | X | X | X | X | X | X | X | X | X | X | X | X | X | - | - |
| Return and Count IP | - | - | X | X | X | X | X | X | X | X | X | X | X | X | X | - |

ECG=Electrocardiogram; ET= Early Termination Visit; CCI [redacted]; IP = Investigational Product; Obs. Follow-up=Post-treatment Observational Follow-up Phase; CCI [redacted]; PGA= Physicians Global Assessment; PMS= Partial Mayo Score; TMS= Total Mayo Score; UC= ulcerative colitis.

- ^a Subjects will be evaluated based on the TMS at the Week 12 Visit and will receive blinded active IP for an additional 40 weeks (Section 4.1).
- ^b At the Week 52 Visit, subjects who have a Mayo endoscopy score ≤1 will have the opportunity to participate in an Extension Phase and will receive apremilast 30 mg BID. With the implementation of Amendment 4, subjects currently in the Extension Phase who are receiving apremilast 40 mg BID will be switched to 30 mg BID at the next scheduled visit.
- ^c Subjects who discontinue from the study prior to the Week 52 Visit, or prior to the Week 104 Visit for subjects participating in the Extension Phase, will have the Early Termination Visit. Subjects who complete the Week 52 Visit and do not participate in the Extension Phase will not have the Early Termination Visit.
- ^d The Post-treatment Follow-up Visit will be conducted approximately 4 weeks after the last dose of IP for all subjects.
- ^e The female subject's chosen form of contraception must be effective by the time the female subject is randomized into the study (for example, hormonal contraception should be initiated at least 28 days before randomization). Contraception education is for males and Females of Child Bearing Potential (FCBP). Pregnancy testing will be performed 7 times during the study for FCBP. Serum pregnancy tests will be performed at Screening and urine pregnancy testing will be done at the Baseline Visit, Week 12, Week 52 (or at the Early Termination Visit if prior to the Week 52 Visit) and all visits during the Extension Phase. In addition, urine pregnancy testing will be done at the Early Termination

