6.14. Study Completion

The End of Trial is defined as either the date of the last visit of the last subject to complete the study, or the date of receipt of the last data point from the last subject that is required for primary, secondary, and/or exploratory analysis, as pre-specified in the protocol and/or the Statistical Analysis Plan, whichever is the later date.

For the purpose of analysis, study completion for an individual subject is defined as reaching the Week 52 Visit. For subjects participating in the Extension Phase, completion of the Extension Phase for an individual subject is defined as completing the Week 104 Visit. Subjects not meeting this definition will be considered early termination subjects. All subjects are required to return for the Post-treatment Observational Follow-up Visit approximately 4 weeks after the last dose of IP.

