### **Extension Phase**

[figure not shown]
At the end of the Blinded Active-treatment Phase (Week 52), subjects who have a Mayo endoscopy score  $\leq 1$  will have the opportunity to participate in the Extension Phase. Subjects participating in the Extension Phase will continue to receive the same treatment assigned during the Blinded Active-treatment Phase for an additional 52 weeks (ie, Weeks 52 to 104).

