### **Post-treatment Observational Follow-up Phase**

All subjects are required to spend 4 weeks in the Post-treatment Observational Follow-up Phase following the last dose of IP.

The study schematic is presented in [Figure 1](#) below.

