#### 12.1.2. All TEAEs

All TEAEs will be summarized by SOC and PT as well as by PT only (in descending order of subject incidence) for the Weeks 0-12 placebo-controlled phase, the Weeks 0-52, Weeks 0-104, and Weeks 52-104 apremilast-exposure periods.

All TEAEs by exposure interval will be summarized for the Weeks 0-12 placebo-controlled phase and the Weeks 0-104 apremilast-exposure period. The exposure intervals are ≤ 2, > 2 – 4, > 4 – 8, > 8 weeks for the Weeks 0-12 placebo-controlled phase, and ≤ 2, > 2 – 4, > 4 – 12, > 12 – 20, > 20 – 28, > 28 – 36, > 36 – 44, > 44 – 52, > 52 – 68, > 68 – 86, > 86 weeks for the Weeks 0-104 apremilast-exposure period. Each subject is counted once in the numerator of a subject incidence or EAIR for each applicable specific TEAE in each exposure interval where an event starts. The denominator of a subject incidence is the number of subjects with the exposure time reaching the lower bound of the particular exposure interval, and the denominator of an EAIR is the sum of the exposure time during the exposure interval (up to the start date [inclusive] of the first occurrence of the specific event for each subject reporting the event in the interval) among the same number of subjects as in the denominator of the corresponding subject incidence.

All TEAEs will be summarized by sex and concomitant use of oral corticosteroids for the Weeks 0-12 placebo-controlled phase and the Weeks 0-104 apremilast-exposure period.

All TEAEs starting after the date of the last dose of IP and up to 28 days after the last dose of IP will be summarized for subjects who enter the observational follow-up phase during the Weeks 0-12 placebo-controlled phase and the Weeks 0-104 apremilast-exposure period. The EAIR will not be provided in this summary.

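### SAP Table 2 gives a Week 52 completer who does not extend no way to be counted as entering follow-up

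*SAP*

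**What the plan says.** - **Entry rule.** In SAP Table 2 the follow-up column sets two conditions for entry, and both must hold. The eCRF must indicate continuation into follow-up, and the subject must have "had data after the last non-follow-up visit (Week 104/Visit 14 or ET visit". The rest of the parenthesis excludes unscheduled visits linked to those same two visits. Follow-up completion is defined separately, as completing the follow-up visit.
- **Visits at exit.** Protocol Table 4, footnote c: "Subjects who complete the Week 52 Visit and do not participate in the Extension Phase will not have the Early Termination Visit".
- **Status at Week 52.** Protocol 6.14: "study completion for an individual subject is defined as reaching the Week 52 Visit". The extension is neither automatic nor open to all. Under the SAP's Extension Phase heading, subjects with a Mayo endoscopy score of 1 or less at Week 52 "will have the opportunity to participate in the Extension Phase".
- **Follow-up is universal.** SAP 4.1: "All subjects are required to spend 4 weeks in the Post-treatment Observational Follow-up Phase following the last dose of IP".
- **Where entry is tabulated.** SAP Section 6 lists Weeks 0-12, 0-52, 12-52 and 52-104, and then the "Post-treatment observational follow-up phase (entered and completed only) within each of the above periods (based on subjects who enter the respective period").
- **Where entry is used again.** SAP 12.1.2: TEAEs that start after the last dose, up to 28 days later, "will be summarized for subjects who enter the observational follow-up phase during the Weeks 0-12 placebo-controlled phase and the Weeks 0-104 apremilast-exposure period".

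**The concern.** The Table 2 list of last non-follow-up visits omits Week 52/Visit 11, which is the planned final on-treatment visit for everyone who does not extend. These subjects finish as the protocol intends and attend follow-up as required, but the entry definition gives them no reference visit.

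Two outputs could be affected. The first is the follow-up disposition summary for Weeks 0-52 and 12-52. The second is the 12.1.2 summary of TEAEs after the last dose. In the visible text this is the one aggregate table that isolates off-drug events, and its denominator is the subjects who enter follow-up. Leaving this group out would not be random with respect to disease, because an endoscopy score above 1 at Week 52 is one of the reasons for not extending.

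**Working it through.** The plan gives no figure to reproduce here; the question is one of definitions. I applied the Table 2 rule literally to each way a subject can leave treatment, taking the eCRF as indicating continuation and a follow-up visit as taking place 28 days later. I then repeated it with Week 52/Visit 11 added for subjects not extending.

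| Exit path | Listed visit available | Entered, literal rule | Entered, Week 52 added |
|---|---|---|---|
| ET before Week 12 | ET | Yes | Yes |
| ET in Weeks 12-52 | ET | Yes | Yes |
| Week 52 completer, no extension | None | No | Yes |
| ET during extension | ET | Yes | Yes |
| Week 104 completer | Week 104 | Yes | Yes |

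Four of the five paths work as written. The one that fails is the Week 52 completer who does not extend: footnote c removes the ET visit, and without the extension there is no Week 104 visit. With the addition all five work.

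Two features of the SAP show that this is an oversight and not a choice:

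1. Section 6 tabulates follow-up within Weeks 0-52 and 12-52. Read literally, subjects whose treatment ends in those periods could enter follow-up only through an ET visit, so those who finish at Week 52 as planned would never be counted.
2. Because completion of follow-up means completing the follow-up visit, a Week 52 completer could be counted as having completed a phase that he or she never entered.

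It does not look like a version mismatch. The SAP is written to the protocol as amended on 20 Jul 2016 and itself makes the extension optional and dependent on endoscopy. The Amendment 4 change log names footnotes b, d and e of the Table of Events, not c.

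**Number affected.** The documents give neither the share reaching Week 52 nor the share extending, so both are assumptions. With 165 randomized:

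number affected = 165 × (share reaching Week 52) × (1 − share of those who extend)

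- Low end: 165 × 0.50 × (1 − 0.70) = 24.75, about 25
- Middle: 165 × 0.65 × (1 − 0.50) = 53.6, about 54
- High end: 165 × 0.80 × (1 − 0.30) = 92.4, about 92

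**The case against.** **The general phrase could govern.** A programmer could treat the parenthesis as an incomplete gloss and take Week 52 as the last non-follow-up visit for these subjects. That is sensible, and it is why the counts may be undefined rather than certainly wrong. But the list is closed, and the unscheduled-visit exclusion repeats the same two visits, so using Week 52 means departing from the text. Two programmers could reach different tables.

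**Table 2 may not govern the AE table.** Section 6 ties the Table 2 definitions to the disposition summaries, and 12.1.2 does not cite Table 2. In ordinary language a Week 52 completer who attends follow-up has entered it. This stands: the effect on the AE table is conditional. Against it, no other definition of entry is visible in the SAP.

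**Safety data are not lost.** A reader might infer that post-treatment events in this group vanish from the safety analysis. The documents do not support that. SAP 5.2 runs the Weeks 0-52 period, for subjects who stop at or before Week 52, to 28 days after the last dose or the last actual follow-up, whichever is first, and ends the Weeks 0-104 period in the same way. Events in that window therefore count in the main TEAE tables, which are not conditioned on entering follow-up. Section 12.1 also lists every AE.

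**The placebo comparison is safe.** Subjects who discontinue in Weeks 0-12 have an ET visit, so the Weeks 0-12 part of the 12.1.2 summary works as written.

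**Size and make-up of the group.** A reader might also infer that the group is known to be large, or consists only of subjects with persistent endoscopic disease. Neither is established. The documents give no count, and because the extension is offered rather than required, eligible subjects who decline belong to the group too.

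**Conclusion.** The gap is real and narrow. As written, Table 2 cannot classify Week 52 completers who do not extend as entering follow-up, so the follow-up disposition counts within Weeks 0-52 and 12-52 are wrong or undefined for them. If 12.1.2 takes its meaning of entry from Table 2, the same subjects are missing from both numerator and denominator in the Weeks 0-104 part of one descriptive safety table, which reports subject incidence without an EAIR. The main TEAE tables, the AE listing, the Weeks 0-12 comparison with placebo and all efficacy results are unaffected. The range of about 25 to 92 subjects is an illustration and rests wholly on the assumed 50-80% reaching Week 52 and 30-70% of those extending.

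**What to change.** In the follow-up entry cell of SAP Table 2, replace the parenthesis with: *(Week 52/Visit 11 for subjects not entering the Extension Phase, Week 104/Visit 14, or ET visit, excluding any unscheduled visits associated with these visits)*. Keeping the exclusion and extending it to Week 52 matters. Without it, an unscheduled visit tied to Week 52 could pass as follow-up data and misclassify subjects in the other direction. In SAP 12.1.2, state that entry to follow-up is as defined in Table 2.

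The cost is one phrase in the table and one cross-reference. No new data are needed and no other analysis changes.

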## 7. **PROTOCOL DEVIATIONS/VIOLATIONS**

Protocol violations and deviations will be summarized for the Screening Phase and Weeks 0-12 using the ITT population, for Weeks 12-52 for subjects who complete Week 12, and for Weeks 52-104 for subjects who enter the Extension Phase.

A listing of all protocol violations and deviations in the study will be provided.

CELGENE PROPRIETARY INFORMATION

## 8. DEMOGRAPHICS AND BASELINE CHARACTERISTICS

Demographics and baseline characteristics will be summarized descriptively using the ITT population. The comparability of the treatment groups for each relevant characteristic will be assessed descriptively in table format; no statistical hypothesis tests will be performed on these characteristics. Subject data listings will be provided.

### 8.1. Demographics and Baseline Characteristics

The following characteristics will be summarized as continuous variables:

- Age (years)
- Baseline body weight (kg)
- Baseline body mass index (BMI; kg/m^2)

The following characteristics will be summarized as categorical variables:

- Age (< 65, ≥ 65 years; < 40, 40 – < 65, 65 – < 75, 75 – < 85, ≥ 85 years)
- Sex (male, female)
- Race (American Indian or Alaska Native, Asian, Black or African American, Native Hawaiian or Other Pacific Islander, White, other, not collected or reported)
- Ethnicity (Hispanic or Latino, not Hispanic or Latino, unknown)
- Region (North America, Western Europe, Eastern Europe/Russia, Australia/New Zealand)
- Baseline body weight (< 55, 55 – < 70, 70 – < 85, 85 – < 100, ≥ 100 kg)
- Baseline BMI (< 18.5, 18.5 – < 25, 25 – < 30, 30 – < 35, 35 – < 40, and ≥ 40 kg/m^2)
- Alcoholic beverages (yes [ $< 1$  drink per week, 1 – 14 drinks per week,  $> 14$  drinks per week], no)
- Tobacco history (never smoked, past smoker, current smoker)

Age will be calculated as (date of informed consent – date of birth + 1) / 365.25 when the full date of birth is collected; otherwise, the age recorded will be used.

### 8.2. Baseline Disease Characteristics

The following baseline disease characteristics will be summarized as continuous variables:

- Duration of UC (years)
- Screening TMS
- Baseline TMS
- Baseline PMS
- Baseline MMS

- Baseline SFS
- Baseline RBS
- Baseline PGA subscore
- Baseline endoscopy subscore
- Baseline SF-12v2 Physical Component Summary (PCS) score
- Baseline SF-12v2 Mental Component Summary (MCS) score

The following baseline disease characteristics will be summarized as categorical variables:

- Duration of UC (< 2, 2 – < 5, 5 – < 10, ≥ 10 years)
- Disease localization (Rectum and sigmoid colon only, left side of colon)
- Baseline extraintestinal manifestations (yes [peripheral arthropathy, axial arthropathies, pyoderma gangrenosum, erythema nodosum, episcleritis, uveitis, primary sclerosing cholangitis, other], no)
- Therapeutic failure with or intolerance to UC medications (yes [never responded, loss of response, partial response, intolerance], no)
- Therapeutic failure with or intolerance to oral aminosalicylates (yes [never responded, loss of response, partial response, intolerance], no)
- Therapeutic failure with or intolerance to budesonide (yes [never responded, loss of response, partial response, intolerance], no)
- Therapeutic failure with or intolerance to systemic corticosteroids (yes [never responded, loss of response, partial response, intolerance], no)
- Therapeutic failure with or intolerance to immunosuppressants (yes [never responded, loss of response, partial response, intolerance], no)
- Contraindication to UC medications (yes [oral aminosalicylates, budesonide, systemic corticosteroids, immunosuppressants], no)
- Concomitant use of oral corticosteroids (as randomized) (yes, no)
- Concomitant use of oral corticosteroids (per clinical database) (yes, no)
- Previous exposure to immunosuppressants (as randomized) (yes, no)
- Previous exposure to immunosuppressants (per clinical database) (yes, no)
- Screening TMS (< 6, 6 – 8, 9 – 11, 12)
- Baseline TMS (< 6, 6 – 8, 9 – 11, 12)
- Baseline endoscopy subscore (0 – 1, 2, 3)

Duration of UC will be calculated as (date of informed consent – date of diagnosis + 1) / 365.25.

### **8.3. Medical History**

Medical history will be coded according to the Medical Dictionary for Regulatory Activities (MedDRA), and summarized based on the ITT population by system organ class (SOC) and preferred term (PT), with SOCs sorted in the standard international order and PTs within each SOC in descending order of frequency, and by PT only in descending order of frequency.

### **8.4. Prior Medications/Procedures**

Prior medications are defined as medications with a start date before the date of the first dose of IP in the study (whether or not the end date is before the date of the first dose of IP). Prior medications that continue on or after the date of the first dose of IP will be also reported as concomitant medications. The Anatomical Therapeutic Chemical (ATC) coding scheme of the World Health Organization Drug Dictionary (WHODD) will be used to group medications into relevant categories. Prior medications will be summarized based on the ITT population by ATC2 level and standardized medication name, with ATC2 levels and standardized medication names within each ATC2 level sorted in descending order of frequency.

Prior procedures are similarly defined. Prior procedures will be coded according to the MedDRA, and summarized based on the ITT population by SOC and PT, with SOCs sorted in the standard international order and PTs within each SOC in descending order of frequency.

## 9. EXTENT OF EXPOSURE TO INVESTIGATIONAL PRODUCT

### 9.1. Treatment Duration

Treatment duration will be summarized for the Weeks 0-12 placebo-controlled phase using the safety population, for the Weeks 0-52 and Weeks 0-104 apremilast-exposure periods using the apremilast subjects as treated population, and for the Weeks 52-104 apremilast-exposure period for subjects who receive at least 1 dose of apremilast after Week 52.

Treatment duration (in weeks) is calculated as (the date of the last dose of IP in the period – the date of the first dose of IP in the period + 1) / 7 and rounded to one decimal place. The date of the last dose of IP in the Weeks 0-12 placebo-controlled phase is defined as the date before IP dispensing at Week 12. The date of the last dose of IP in the Weeks 0-52 apremilast-exposure period and the date of the first dose of IP in the Weeks 52-104 apremilast-exposure period are defined as the date before and the date of, respectively, IP dispensing at Week 52.

Treatment duration will be summarized as a continuous variable, and as a categorical variable with the following exposure intervals:

- Weeks 0-12 placebo-controlled phase:  $\leq 4$ ,  $> 4 - 8$ ,  $> 8 - 12$ ,  $> 12$  weeks
- Weeks 0-52 apremilast-exposure period:  $\leq 4$ ,  $> 4 - 8$ ,  $> 8 - 12$ ,  $> 12 - 20$ ,  $> 20 - 28$ ,  $> 28 - 36$ ,  $> 36 - 44$ ,  $> 44 - 52$ , and  $> 52$  weeks
- Weeks 0-104 apremilast-exposure period:  $\leq 4$ ,  $> 4 - 8$ ,  $> 8 - 12$ ,  $> 12 - 20$ ,  $> 20 - 28$ ,  $> 28 - 36$ ,  $> 36 - 44$ ,  $> 44 - 52$ ,  $> 52 - 68$ ,  $> 68 - 86$ ,  $> 86 - 104$ ,  $> 104$  weeks
- Weeks 52-104 apremilast-exposure period (intervals denote the number of weeks relative to the date of the first dose of IP in the Weeks 52-104 apremilast-exposure period as defined above):  $\leq 16$ ,  $> 16 - 34$ ,  $> 34 - 52$ ,  $> 52$  weeks

A subject data listing of study drug records will be provided.

### 9.2. Treatment Compliance

As part of the routine recording of the amount of IP taken by each subject, the numbers of tablets dispensed and returned will be recorded at each visit. These records will be used to calculate treatment compliance. Treatment compliance will be summarized for the Weeks 0-12 placebo-controlled phase using the ITT population, for Weeks 12-52 for subjects who receive at least 1 dose of apremilast after Week 12 (defined as the date of the last dose of apremilast in the study no earlier than the date of IP dispensing at Week 12), and for Weeks 52-104 for subjects who receive at least 1 dose of apremilast after Week 52.

The compliance rate (%) for each subject will be computed as 100 times the total number of tablets taken (the total number of tablets dispensed minus the total number of tablets returned) over the period divided by the intended total number of tablets that should have been taken over the same period (defined by the first and last IP dose dates in the period). The date of the last dose of IP in the Weeks 0-12 placebo-controlled phase and the date of the first dose of IP in Weeks 12-52 are defined as the date before and the date of, respectively, IP dispensing at Week

12. The date of the last dose of IP in Weeks 12-52 and the date of the first dose of IP in Weeks 52-104 are defined as the date before and the date of, respectively, IP dispensing at Week 52.

Treatment compliance rate will be summarized as a continuous variable, and as a categorical variable with the following categories: < 75%, 75% – 120%, and > 120%.

A subject data listing of drug accountability records will be provided.

CELGENE PROPRIETARY INFORMATION

